17.1.1. ALL AEs

AEs will be presented by SOC, High Level Term (HLT), and PT for AE incidence and number of events. AEs will also be presented by maximum severity and by strongest relationship to the study medication as specified in the sections below.

AEs that occurred in $\geq 5\%$ of subjects will be summarized by SOC and PT.

17.1.1.1. Severity

Severity is classed as mild/ moderate/ severe (increasing severity). AEs with a missing severity will be summarized as missing severity. If a subject reports an AE more than once within the same SOC/ PT, the

Document: Documentation\SAP

Author:

Version Number:

Final V1.0

Version Date:

27FEB2019

Template No: CS_TP_BS016 Revision 4
 Effective Date: 01Apr2016

Reference: CS_WI_BS005

Copyright © 2009, 2010, 2012, 2016 Quintiles Transnational Corp. All rights reserved.

The contents of this document are confidential and proprietary to Quintiles Transnational Corp. Unauthorized use, disclosure or reproduction is strictly prohibited.

AE with the worst severity will be used in the corresponding severity summaries. For this summary, AEs will be presented by SOC and PT.

17.1.1.2. Relationship to Study Medication

Relationship, as indicated by the investigator, is classed as “not related”/ “possible”/ “probable”/ “definite” (increasing strength of relationship). A “related” AE is defined as an AE with a relationship to the study medication of “possible”, “probable” or “definite”. A “not related” AE is defined as an AE with a relationship to the study medication of “not related”. AEs with a missing relationship to the study medication will be regarded as “related” to the study medication. If a subject reports the same AE more than once within the same SOC/ PT, the AE with the strongest relationship to study medication will be used in the corresponding relationship summaries. For this summary, AEs will be presented by SOC and PT.

17.1.2. AEs LEADING TO DISCONTINUATION OF STUDY MEDICATION

AEs leading to permanent discontinuation of study medication are AEs for which “Drug Withdrawn” is selected for “Action Taken with Study Treatment” on the AE CRF page. A summary of AEs leading to discontinuation of study medication by SOC and PT will be presented.

17.1.3. AEs LEADING TO DISCONTINUATION FROM THE STUDY

AEs leading to discontinuation from the study are AEs with “Caused Study Discontinuation” = “Yes” on the AE CRF page. A summary of AEs leading to discontinuation from the study by SOC and PT will be presented.

17.1.4. SERIOUS ADVERSE EVENTS

SAEs are those AEs recorded as “Serious” on the AE CRF page. Summaries of serious AEs and non-serious AEs by SOC and PT will be prepared.

17.1.5. ADVERSE EVENTS LEADING TO DEATH

AEs leading to death are those AEs which are recorded as having an outcome of “Fatal” on the AE CRF page. A summary of AEs leading to death by SOC and PT will be prepared.

17.1.6. ADVERSE EVENTS BY SUBGROUP

As stated above, overall incidence summaries will be presented by the subgroups of region, sex, age, prior number of hospitalizations for acute exacerbation of schizophrenia, and duration of schizophrenia. The same subgroup factors will also apply to the by-subgroup summaries for the following events:

- All AEs, by SOC and PT

Document: Documentation\SAP

Author:

Version Number:
 Version Date:

Final V1.0
 27FEB2019

Template No: CS_TP_BS016 Revision 4
 Effective Date: 01Apr2016

Reference: CS_WI_BS005

Statistical Analysis Plan

- SAEs, by SOC and PT
- AEs leading to discontinuation of study medication, by SOC and PT
- AEs leading to discontinuation from the study, by SOC and PT

In addition, all AEs (by SOC and PT) will be summarized by the BMI (kg/m²) category at both DB baseline and OL baseline:

- o Underweight: <18.5
- o Normal: 18.5 to <25.0
- o Overweight: 25.0 to <30.0
- o Obese: >=30.0

17.1.1. ADVERSE EVENTS POST LAST DOSE OF EXTENSION STUDY MEDICATION

Adverse events that started after last dose of extension study medication until 9 days after the last dose will be summarized separately.

17.2. LABORATORY EVALUATIONS

Laboratory data to be reported for this study include hematology, serum chemistry (including lipid panel and thyroid panel), urinalysis, urine drug screening, and urine and serum pregnancy test (only listed).

Presentations will use international system of units (SI).

Quantitative laboratory measurements reported as “< X”, i.e. below the lower limit of quantification (BLQ), or “> X”, i.e. above the upper limit of quantification (ULQ), will be converted to X for the purpose of quantitative summaries, but will be presented as recorded, i.e. as “< X” or “> X” in listings.

The following summaries will be provided for laboratory data:

- By visit summary of observed values and changes from baseline for continuous data in hematology, chemistry, and urinalysis. Prolactin results will be summarized separately by gender. Glucose and lipid panel results will be summarized separately by fasting status.
- By visit summary of the number and percentage of subjects in each outcome category for categorical data in urinalysis and urine drug screening. For urine drug screening, the results will be reported as “Positive”/ “Negative”.
- Shift in lab results (chemistry, hematology, urinalysis) from baseline to post baseline extension visits according to the reference range criteria provided by the central laboratory.
- Summary of the number and percentage of subjects with at least one post-OL baseline PCS value for selected laboratory parameters (Table 3). The period of evaluation includes both the OL treatment period and the OL follow-up period.

Document: Documentation\SAP

Author:

Version Number:

Final V1.0

Version Date:

27FEB2019

Template No: CS_TP_BS016 Revision 4
 Effective Date: 01Apr2016

Reference: CS_WI_BS005

Copyright © 2009, 2010, 2012, 2016 Quintiles Transnational Corp. All rights reserved.

The contents of this document are confidential and proprietary to Quintiles Transnational Corp. Unauthorized use, disclosure or reproduction is strictly prohibited.

Both the DB baseline and the OL baseline will be used in the calculation of change values and presenting the shift summaries.

All laboratory data will be provided in data listings, with the values outside the reference ranges flagged.

Table 3. PCS Criteria for Laboratory Parameters – SI Units

Category Parameter Name Age/Gender Restriction, if any	PCS Low	PCS High
HEMATOLOGY		
WBC	$\leq 2.8 \times 10^9/L$	$\geq 16 \times 10^9/L$
Neutrophils (abs)	$< 0.5 \times 10^9/L$	$> 13.5 \times 10^9/L$
Lymphocytes (abs)	N/A	$> 12 \times 10^9/L$
Monocytes (abs)	N/A	$> 2.5 \times 10^9/L$
Eosinophils (abs)	N/A	$> 1.6 \times 10^9/L$
Basophils (abs)	N/A	$> 1.6 \times 10^9/L$
Neutrophils (relative)	≤ 0.15	> 0.85
Lymphocytes (relative)	N/A	≥ 0.75
Monocytes (relative)	N/A	≥ 0.15
Eosinophils (relative)	N/A	≥ 0.10
Basophils (relative)	N/A	≥ 0.10
Hemoglobin		
Male	$\leq 115 \text{ g/L}$	$\geq 190 \text{ g/L}$
Female	$\leq 95 \text{ g/L}$	$\geq 175 \text{ g/L}$
Hematocrit		
Male	≤ 0.37	≥ 0.60
Female	≤ 0.32	≥ 0.54
RBC	$\leq 3.5 \times 10^{12}/L$	$\geq 6.4 \times 10^{12}/L$
Platelet Count	$\leq 75 \times 10^9/L$	$\geq 700 \times 10^9/L$
SERUM CHEMISTRY		
Sodium	$< 130 \text{ mmol/L}$	$> 150 \text{ mmol/L}$
Potassium	$< 3 \text{ mmol/L}$	$> 5.5 \text{ mmol/L}$
Chloride	$\leq 90 \text{ mmol/L}$	$\geq 118 \text{ mmol/L}$
Calcium	$< 1.75 \text{ mmol/L}$	$\geq 3.1 \text{ mmol/L}$
Phosphate	$< 0.65 \text{ mmol/L}$	$> 1.65 \text{ mmol/L}$
Bicarbonate	$< 15.1 \text{ mmol/L}$	$> 34.9 \text{ mmol/L}$
Magnesium	$< 0.4 \text{ mmol/L}$	$> 1.23 \text{ mmol/L}$
AST (IU/L)	N/A	$\geq 3 \times \text{ULN}$
ALT (IU/L)	N/A	$\geq 3 \times \text{ULN}$
Alkaline Phosphatase (IU/L)	N/A	$\geq 1.5 \times \text{ULN}$
CK (IU/L)	N/A	$> 2.5 \times \text{ULN}$
Creatinine	N/A	$\geq 177 \text{ umol/L}$
BUN	N/A	$\geq 10.7 \text{ mmol/L}$
Total bilirubin (mg/dL)	N/A	$\geq 34.2 \text{ umol/L OR } > 2 \times \text{ULN}$
Total protein	$\leq 45 \text{ g/L}$	$\geq 100 \text{ g/L}$
Albumin	$\leq 25 \text{ g/L}$	N/A

Document: Documentation\SAP

Author:

Version Number:

Final V1.0

Version Date:

27FEB2019

Template No: CS_TP_BS016 Revision 4

Reference: CS_WI_BS005

Effective Date: 01Apr2016

Copyright © 2009, 2010, 2012, 2016 Quintiles Transnational Corp. All rights reserved.

The contents of this document are confidential and proprietary to Quintiles Transnational Corp. Unauthorized use, disclosure or reproduction is strictly prohibited.

Total Cholesterol	N/A	> 7.76 mmol/L
HDL-Cholesterol	< 0.78 mmol/L	N/A
LDL-Cholesterol	N/A	> 4.14 mmol/L
Triglycerides	N/A	> 3.42 mmol/L
Uric acid		
Male	N/A	> 595 umol/L
Female	N/A	> 476 umol/L
Glucose	< 2.78 mmol/L	> 13.9 mmol/L
HbA1c	N/A	≥ 0.075
Prolactin	N/A	≥ 5 x ULN
URINALYSIS		
RBC	N/A	> 25 hpf
WBC	N/A	> 25 hpf

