17.3. ECG EVALUATIONS

Results from the central ECG (Electrocardiogram) will be included in the reporting of this study.

The following ECG parameters will be reported for this study:

- PR Interval (msec)
- RR Interval (msec)
- QRS Duration (msec)
- QRS Axis (deg)
- QT Interval (msec)
- QTcF Interval (msec) [derived]
- QTcB Interval (msec) [derived]
- Heart rate (HR) (beats/min)
- ECG findings
- Overall assessment of ECG (investigator's judgment):
 - o Normal
 - o Abnormal, Significant
 - o Abnormal, Insignificant

Document: Documentation\SAP

Author:

Version Number:
Version Date:

Final V1.0
27FEB2019

Template No: CS_TP_BS016 Revision 4
Effective Date: 01Apr2016

Reference: CS_WI_BS005

Statistical Analysis Plan

The following summaries will be provided for ECG data:

- By visit summary of observed values and changes from baseline (for quantitative measurements)
- Number and percentage of subjects with QTc levels in each of the QTc categories
- By visit summary of ECG overall assessment results
- Shift in ECG overall assessments from baseline to post-OL baseline extension visits and LOCF.

Both the DB baseline and the OL baseline will be used in the calculation of change values and presenting the shift summaries.

The number and percentage of subjects with QTc values in the following categories will be identified. The same criteria apply to both QTcF and QTcB.

- > 450 msec at any post OL baseline time point (including unscheduled visits) not present at DB baseline
- > 450 msec at any post OL baseline time point (including unscheduled visits) not present at OL baseline
- > 480 msec at any post OL baseline time point (including unscheduled visits) not present at DB baseline
- > 480 msec at any post OL baseline time point (including unscheduled visits) not present at OL baseline
- > 500 msec at any post OL baseline time point (including unscheduled visits) not present at DB baseline
- > 500 msec at any post OL baseline time point (including unscheduled visits) not present at OL baseline
- ≥ 30 msec increase from DB baseline for at least one post OL baseline measurement (including unscheduled visits) and < 60 msec increase from DB baseline for all post OL baseline measurements (including unscheduled visits)
- ≥ 30 msec increase from OL baseline for at least one post OL baseline measurement (including unscheduled visits) and < 60 msec increase from OL baseline for all post OL baseline measurements (including unscheduled visits)

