17.4. VITAL SIGNS

The following vital signs measurements will be reported for this study:

- Supine Systolic Blood Pressure (mmHg)
- Standing Systolic Blood Pressure (mmHg)
- Supine Diastolic Blood Pressure (mmHg)
- Standing Diastolic Blood Pressure (mmHg)
- Supine Pulse Rate (beats/min)
- Standing Pulse Rate (beats/min)
- Respiratory Rate (breaths/min)
- Temperature (°C)
- Weight (kg)
- BMI (kg/m²)
- Waist Circumference (cm)

The following summaries will be provided for vital signs data:

- Observed value and change from baseline by visit
- Observed value and change from baseline by visit by BMI category at both DB baseline and OL baseline:
 - o Underweight: <18.5
 - o Normal: 18.5 to <25.0
 - o Overweight: 25.0 to <30.0
 - o Obese: >=30.0
- Number and percentage of subjects with at least one post-OL baseline PCS value for selected vital signs parameters (Table 4). The period of evaluation includes both OL treatment period and OL follow-up period.

Both the DB baseline and the OL baseline will be used in the calculation of change values.

All vital signs data will be provided in data listings.

Document: Documentation\SAP

Author:

Version Number:
 Version Date:

Final V1.0
 27FEB2019

Template No: CS_TP_BS016 Revision 4
 Effective Date: 01Apr2016

Reference: CS_WI_BS005

Table 4. PCS Criteria for Vital Signs Parameters

Parameter Name	PCS Low	PCS High
Systolic Blood Pressure (mmHg)	Value ≤ 90 and ≥ 20 decrease from baseline	Value ≥ 180 and ≥ 20 increase from baseline
Diastolic Blood Pressure (mmHg)	Value ≤ 50 and ≥ 15 decrease from baseline	Value ≥ 105 and ≥ 15 increase from baseline
Pulse Rate (beats/min)	Value ≤ 50 and ≥ 15 decrease from baseline	Value ≥ 120 and ≥ 15 increase from baseline
Weight (kg)	$\geq 7\%$ decrease from baseline	$\geq 7\%$ increase from baseline
Temperature ($^{\circ}\text{C}$)	NA	Value $\geq 38.3^{\circ}\text{C}$ and $\geq 0.8^{\circ}\text{C}$ increase from baseline

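### The laboratory PCS table in SAP 17.2 has no baseline condition, so it does not separate new potentially clinically significant values from pre-existing ones

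*SAP*

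**What the plan says.** SAP 17.2 lists four laboratory summaries. The one at issue is the "Summary of the number and percentage of subjects with at least one post-OL baseline PCS value for selected laboratory parameters". It adds that "The period of evaluation includes both the OL treatment period and the OL follow-up period". Every row of Table 3 is a fixed value or a multiple of the upper limit of normal (ULN); none mentions a change from baseline or the subject's baseline status. SAP 6.4 feeds unscheduled values into the PCS derivation and adds no baseline exclusion.

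The two baselines do enter the laboratory section, but only for other outputs: "Both the DB baseline and the OL baseline will be used in the calculation of change values and presenting the shift summaries". The shift tables are built "according to the reference range criteria provided by the central laboratory", and the listings likewise flag reference-range departures.

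Other safety sections use a different rule. SAP 17.3 counts a QTc threshold as "> 450 msec at any post OL baseline time point (including unscheduled visits) not present at DB baseline" and separately as "> 450 msec at any post OL baseline time point (including unscheduled visits) not present at OL baseline", and repeats the pair at 480 and 500 msec. In Table 4 of SAP 17.4 every vital-sign PCS row requires a change; the low limit for systolic pressure, for example, reads "Value ≤ 90 and ≥ 20 decrease from baseline".

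**The concern.** The study has no control arm, so a subject's own baseline is the main reference for reading an abnormality rate. Subjects can plausibly enter beyond a Table 3 limit. Exclusion criterion 2 (Protocol 8.2) depends on the judgement of the investigator and medical monitor rather than on the PCS limits, and Protocol 10.3.1 allows stable treatment for mild chronic conditions. A subject with long-standing high triglycerides, LDL-cholesterol or HbA1c would then count as a PCS case in the extension.

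At stake is the reading of one descriptive safety table. Its percentages could be taken as the frequency of laboratory abnormalities arising on SEP-363856 when an unknown part was there beforehand.

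**Working it through.** **No stated figure to reproduce.** The documents give no expected PCS rate, and the sample size of about 180 is anticipated roll-over rather than a calculation. The check is a comparison of rules followed by an illustration.

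**Comparison of rules**

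| Output | Threshold used | Baseline condition |
|---|---|---|
| Laboratory PCS (17.2, Table 3) | PCS limit | None |
| Laboratory shifts (17.2) | Reference range | DB and OL baseline |
| QTc >450, >480, >500 msec (17.3) | Same threshold | Not present at DB baseline; separately, at OL baseline |
| Vital-sign PCS (17.4, Table 4) | PCS limit | Change from baseline in every row |

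**Do the shift tables fill the gap?** Take prolactin, with a PCS limit of 5 x ULN or above. One subject moves from 1.5 to 6 x ULN; another stays at 6 x ULN throughout. Both are high at baseline and high afterwards in the shift table, and both are PCS cases. Only the first is a new crossing, and neither output shows it. The same holds for AST and ALT at 3 x ULN.

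**Illustration.** Inputs: N = 180 (SAP 3.3). Three quantities are assumed because the documents do not give them:
- b, the share beyond the limit at baseline (1-10%);
- s, the share of those beyond it again after OL baseline (50-100%);
- e, the risk of newly crossing among the rest (2-5%).

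All subjects are taken to have baseline and later values.

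Count under SAP 17.2 = N·b·s + N·(1 − b)·e. Rate of new values = e, on denominator N·(1 − b). The excess of the reported rate over e is b·s + (1 − b)·e − e = b·(s − e).

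| b | s | e | Pre-existing | New | SAP 17.2 rate | New rate | Pre-existing share |
|---|---|---|---|---|---|---|---|
| 1% | 50% | 5% | 0.90 | 8.91 | 9.81/180 = 5.5% | 8.91/178.2 = 5.0% | 9% |
| 5% | 80% | 2% | 7.20 | 3.42 | 10.62/180 = 5.9% | 3.42/171 = 2.0% | 68% |
| 10% | 100% | 2% | 18.00 | 3.24 | 21.24/180 = 11.8% | 3.24/162 = 2.0% | 85% |

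The first and last rows are the extremes of the assumed range: the excess is 0.01 × (0.50 − 0.05) = 0.45 percentage points and 0.10 × (1.00 − 0.02) = 9.8 points. If nobody newly crossed (e = 0), the planned table would still report b·s, from 0.5% to 10%.

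**The case against.** The best case for the plan is that the table claims no more than it delivers. SAP 17.2 never calls the count treatment-emergent, and every new case is in it. By-visit changes and shift tables against both baselines, with full listings, surround it. For the ULN-multiple limits, a subject beyond the PCS limit at baseline is already high and cannot enter the normal-to-high cell, so that cell is free of pre-existing PCS cases. Clinically significant abnormalities found after dosing are recorded as adverse events (Protocol 12.2), and SAP 17.1 tabulates only events starting at or after the first extension dose. The table templates mentioned in SAP section 8 are not available here and might carry a baseline row or footnote.

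Much of this stands. It confines the gap to one supplementary table, which the protocol's own laboratory analysis (15.3.6.2) does not include. It does not close the gap. The normal-to-high cell counts any crossing of the reference limit, however small, and misses subjects who start mildly high and then cross the PCS limit. Adverse event recording rests on the investigator's judgement, not on Table 3. Listings would allow the split only by hand.

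Some stronger readings are tempting but not supported:
- A reader might infer that the counts say nothing about abnormalities arising on the drug. They contain those cases; they do not isolate them.
- A reader might infer that prolactin counts mainly reflect earlier antipsychotics. Subjects may not have taken other schizophrenia medication during Study SEP361-201 (Protocol 8.1, criterion 3), and other antipsychotics are prohibited in the extension (10.3.3). A carry-over case would still need 5 x ULN or more at Week 1 of the extension or later, after the four-week double-blind period plus about another week.
- A reader might take SAP 17.3 as precedent for an at-risk denominator. It sets the not-present condition but states no such denominator.

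**Conclusion.** The point holds as a cheap improvement to a descriptive table. The laboratory PCS count mixes new and pre-existing values, and no summary described in the SAP isolates new crossings of the PCS limits. The SAP already makes that distinction for QTc and builds baseline change into the vital-sign criteria; it gives no reason for treating laboratory values differently.

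The size is unknown. A reader might quote a multiplier from the illustration, but any multiplier rests on an assumed baseline prevalence and persistence. The effect could be trivial or could dominate the count, and the planned table cannot show which. No inference depends on it, since SAP section 17 makes no statistical comparisons of safety data.

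**What to change.** Keep the existing count in SAP 17.2 and add, for each Table 3 parameter and separately for its low and high limits:

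- the number and percentage of subjects with a post-OL baseline PCS value not present at DB baseline;
- the number and percentage with a post-OL baseline PCS value not present at OL baseline.

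The condition follows the QTc rule in SAP 17.3. State the denominator explicitly: subjects with a value at that baseline that does not meet the limit.

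Both baselines are needed. The SEP-SEP group (SAP Appendix 1) took SEP-363856 before OL baseline, so conditioning on OL baseline alone would hide abnormalities that arose on the drug in Study SEP361-201. For the PBO-SEP group, OL baseline is the last value before the drug.

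The cost is programming and layout: two baselines across three presentation groups (PBO-SEP, SEP-SEP, ALL EXT) make 2 × 3 = 6 added columns, with denominators that differ by parameter. No new data are needed. If the SAP is not reissued, its section 20 allows the change to be described and justified in the final report.

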17.3. ECG EVALUATIONS

Results from the central ECG (Electrocardiogram) will be included in the reporting of this study.

The following ECG parameters will be reported for this study:

- PR Interval (msec)
- RR Interval (msec)
- QRS Duration (msec)
- QRS Axis (deg)
- QT Interval (msec)
- QTcF Interval (msec) [derived]
- QTcB Interval (msec) [derived]
- Heart rate (HR) (beats/min)
- ECG findings
- Overall assessment of ECG (investigator's judgment):
 - o Normal
 - o Abnormal, Significant
 - o Abnormal, Insignificant

Document: Documentation\SAP

Author:

Version Number:
Version Date:

Final V1.0
27FEB2019

Template No: CS_TP_BS016 Revision 4
Effective Date: 01Apr2016

Reference: CS_WI_BS005

Statistical Analysis Plan

The following summaries will be provided for ECG data:

- By visit summary of observed values and changes from baseline (for quantitative measurements)
- Number and percentage of subjects with QTc levels in each of the QTc categories
- By visit summary of ECG overall assessment results
- Shift in ECG overall assessments from baseline to post-OL baseline extension visits and LOCF.

Both the DB baseline and the OL baseline will be used in the calculation of change values and presenting the shift summaries.

The number and percentage of subjects with QTc values in the following categories will be identified. The same criteria apply to both QTcF and QTcB.

- > 450 msec at any post OL baseline time point (including unscheduled visits) not present at DB baseline
- > 450 msec at any post OL baseline time point (including unscheduled visits) not present at OL baseline
- > 480 msec at any post OL baseline time point (including unscheduled visits) not present at DB baseline
- > 480 msec at any post OL baseline time point (including unscheduled visits) not present at OL baseline
- > 500 msec at any post OL baseline time point (including unscheduled visits) not present at DB baseline
- > 500 msec at any post OL baseline time point (including unscheduled visits) not present at OL baseline
- ≥ 30 msec increase from DB baseline for at least one post OL baseline measurement (including unscheduled visits) and < 60 msec increase from DB baseline for all post OL baseline measurements (including unscheduled visits)
- ≥ 30 msec increase from OL baseline for at least one post OL baseline measurement (including unscheduled visits) and < 60 msec increase from OL baseline for all post OL baseline measurements (including unscheduled visits)
- ≥ 60 msec increase from DB baseline for at least one post OL baseline measurement (including unscheduled visits)
- ≥ 60 msec increase from OL baseline for at least one post OL baseline measurement (including unscheduled visits)

Document: Documentation\SAP

Author:

Version Number:

Final V1.0

Version Date:

27FEB2019

Template No: CS_TP_BS016 Revision 4
 Effective Date: 01Apr2016

Reference: CS_WI_BS005

Copyright © 2009, 2010, 2012, 2016 Quintiles Transnational Corp. All rights reserved.

The contents of this document are confidential and proprietary to Quintiles Transnational Corp. Unauthorized use, disclosure or reproduction is strictly prohibited.

All ECG parameters, overall interpretation, and findings will be provided in data listings.

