15.3.6.3. ECGs

Absolute values and changes from Baseline in ECG parameters will be summarized. In addition, the number and percentage of subjects with elevated QTc intervals (> 450 msec, > 480 msec, and > 500 msec) and changes from baseline in QTc intervals ≥ 30 msec and ≥ 60 msec will be summarized. Fridericia’s correction (QTcF) and Bazett’s correction (QTcB) will be used for QT interval correction. Both the DB baseline of study SEP361-201 and the OL baseline of study SEP361-202 will be used in the calculation of change values.

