3.7. CHANGES TO ANALYSIS FROM PROTOCOL

- The protocol specified that for subjects *assigned* to double-blind SEP-363856, clinical response will be evaluated using the Day 29 data of study 361-201, against the DB baseline, and for subjects *assigned* to double-blind placebo, clinical response will be evaluated using the Day 29 data of study 361-202, against the OL baseline. Rather than the randomized treatment assigned to subjects, the analysis will be based on the *actual treatment received* during study 361-201. In addition, rather than using different baselines based on 361-201 treatment, DB baseline will be used for all subjects rolling over to 361-202, irrespective of the treatment they received in 361-201.
- The protocol specified that PANSS response rate will be calculated based on the DB baseline for subjects assigned to double-blind SEP-363856 and the OL baseline for subjects assigned to double-blind placebo. Rather than using different baselines based on 361-201 treatment, DB baseline will be used for all subjects rolling over to 361-202, irrespective of the treatment they received in 361-201.

Document: Documentation\SAP

Author:

Version Number:

Final V1.0

Version Date:

27FEB2019

Template No: CS_TP_BS016 Revision 4
 Effective Date: 01Apr2016

Reference: CS_WI_BS005

- The protocol specified that the total score will be used as a summary measure of the subject's ratings on the Simpson-Angus Rating Scale (SAS). Rather than the total score, the mean score will be used, which is calculated as the average of the 10 item scores.
- The protocol specified that one relapse criterion is emergence of suicidal ideation, homicidal ideation and/or risk of harm to self or others. The term 'suicidal ideation' is to be replaced by 'suicidality' and the term 'homicidal ideation' replaced by 'homicidality'. This is because the search criteria for AEs and C-SSRS data that meet this relapse criterion (see appendix 3) cover both suicidal ideation and suicidal behavior, and both homicidal ideation and homicidal behavior.

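### SAP 17.3 tabulates only QTc exceedances that were absent at a baseline, so the protocol's unconditional counts above 450, 480 and 500 msec are in no described summary, and SAP 3.7 does not list the change

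*SAP*

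**What the plan says.** Protocol 15.3.6.3 plans to summarise "the number and percentage of subjects with elevated QTc intervals" at three limits: above 450, 480 and 500 msec. It attaches no baseline condition to these counts and gives no time point. The DB and OL baselines are named for a different purpose; they "will be used in the calculation of change values".

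SAP 17.3 turns each limit into two rows, applied to both QTcF and QTcB. At the lowest limit they read "> 450 msec at any post OL baseline time point (including unscheduled visits) not present at DB baseline" and "> 450 msec at any post OL baseline time point (including unscheduled visits) not present at OL baseline". The 480 and 500 msec rows have the same form, so all six threshold rows carry a baseline condition. They feed the one categorical QTc summary: "Number and percentage of subjects with QTc levels in each of the QTc categories".

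The other ECG summaries in SAP 17.3 are by-visit descriptive statistics, by-visit overall assessment, and shifts in overall assessment. Individual values go into listings. SAP 3.7 lists four changes from the protocol: the baseline for clinical response, the baseline for PANSS response, SAS mean instead of total score, and the suicidality wording. None concerns ECG.

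**The concern.** The two documents count different things. The natural reading of the protocol is how many subjects had a QTc above each limit. The SAP asks how many had one that was not already there at a chosen baseline. Both are useful, but the second does not yield the first.

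The design makes the difference relevant. Exclusion criterion 2 in protocol 8.2 is a judgement with no numeric QTc limit, so subjects above 450 msec can enter. For subjects who took SEP-363856 in Study SEP361-201, OL baseline follows four weeks on drug. Someone who crossed 450 msec during those weeks and stayed above it is left out of the OL-baseline row. The DB-baseline row keeps that subject but leaves out anyone above the limit before first treatment.

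SAP 17.2 treats laboratory outliers differently: it counts subjects with at least one potentially clinically significant value after OL baseline, and the Table 3 criteria carry no baseline condition. SAP 3.7 records changes as small as SAS total to SAS mean, so a reader would expect this one there too.

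At stake is a descriptive safety count in a study whose primary objective is long-term safety. No hypothesis test depends on it.

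**Working it through.** The plan states no QTc count or QTc prevalence, so there is no figure to reproduce. The check has two parts.

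**1. Which subjects each rule counts.** Fix one limit. These are the four patterns with an exceedance after OL baseline (1 = counted):

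| Above limit at DB baseline | Above limit at OL baseline | Unconditional | SAP, DB version | SAP, OL version |
|---|---|---|---|---|
| No | No | 1 | 1 | 1 |
| No | Yes | 1 | 1 | 0 |
| Yes | No | 1 | 0 | 1 |
| Yes | Yes | 1 | 0 | 0 |

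The unconditional rule counts all four patterns and each SAP version counts two. For each version:

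unconditional count = SAP count + subjects above the limit at that baseline and again after OL baseline.

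The SAP count therefore cannot exceed the unconditional one. It is strictly lower only if the added term is at least one subject. That term is not tabulated, so the unconditional count cannot be rebuilt from the two SAP rows.

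**2. How large the added term might be.** From the documents: about 180 subjects (protocol 15.1) and eight scheduled post-baseline ECGs (protocol Table 2: Weeks 1, 4, 8, 12, 16, 20, 24 and 26). Assumed: normal QTc, mean 410-420 msec, SD 20, equal correlation r of 0.5-0.7 between visits, no drug effect.

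For limit L let z = (L − mean)/20, and let p(s) = Φ((z − √r·s)/√(1 − r)) be the chance that one reading is at or below L, given the subject's own level s. Averaging over a standard normal s:

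- any exceedance = E[1 − p⁸]
- new relative to one baseline = E[p(1 − p⁸)]
- missing from both versions = E[(1 − p)²(1 − p⁸)]

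Results for 450 msec, from simulation of 400,000 subjects (numerical integration of these formulas agrees within 0.2 percentage points):

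| Mean | r | Any | New | Difference (points) | Of 180 |
|---|---|---|---|---|---|
| 410 | 0.5 | 11.6% | 10.2% | 1.4 | 2.5 |
| 410 | 0.7 | 8.8% | 7.1% | 1.7 | 3.1 |
| 415 | 0.7 | 14.2% | 10.9% | 3.3 | 5.9 |
| 420 | 0.5 | 27.4% | 22.3% | 5.1 | 9.2 |
| 420 | 0.7 | 21.0% | 15.4% | 5.6 | 10.1 |

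The last column is the difference × 180/100. Subjects missing from both versions at 450 msec number about 0.6-4.9 of 180. At 480 msec the expected loss is at most 0.13 of 180 subjects per version, and at 500 msec it is 0.00.

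A check that does not use the normal model: let b be the share above the limit at baseline and q the chance of exceeding it again. The chance that at least one of 180 subjects is dropped is 1 − (1 − bq)¹⁸⁰. With q = 0.5-0.8 this is 0.59-0.76 at b = 1% and 0.09-0.13 at b = 0.1%. For a rarely exceeded limit the two counts may well coincide.

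**The case against.** The strongest reply is that the protocol left the rule open. It names no time point and does not mention on-treatment values, so the SAP had to define the count, and a definition relative to baseline is a reasonable way to do it. That is fair about the wording and is a reason to keep the new-onset rows. It does not explain why a condition absent from the protocol is missing from SAP 3.7, or why the unconditional count is not shown beside it.

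The data are not lost. All ECG values are listed. The by-visit summaries include the maximum under the output conventions in SAP Appendix 1, so a high value at a scheduled visit would be visible. Clinically significant ECG findings are recorded as AEs under protocol 12.2. This stands as mitigation, but a maximum shows that a limit was passed, not by how many subjects. The table templates are not in the documents, so the claim here is limited to the summaries that the SAP describes.

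A reader might also infer that the protocol's count of rises of at least 30 msec is lost, because the SAP row requires all rises to stay below 60 msec. It is not lost. For each baseline the 30-to-below-60 row and the 60-or-more row are exclusive and together cover every rise of at least 30 msec, so their sum is the protocol's count.

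**Conclusion.** The point holds as a minor one. The SAP replaces an unconditional count with a new-onset count at all three limits, does not declare it in SAP 3.7, and describes no summary that gives the unconditional figure.

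Three stronger readings are not supported:

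- **That the reported count must be lower.** It is equal or lower, depending on baseline exceedances that the documents do not give.
- **That all three limits are affected alike.** Under the assumed inputs the effect is at 450 msec: about 1.4-5.6 percentage points, or 2-10 of 180 subjects per version. At 480 and 500 msec it is near zero. Those two results rest on normal tails and would change if a few subjects had markedly long QTc at baseline.
- **That a subject above a limit at baseline disappears.** Someone above it at one baseline only is still counted in the other version. Someone who moves from above 450 at baseline to above 480 or 500 msec is counted at the higher limit. A rise of at least 30 msec appears in a change row. Missing from both threshold rows for a limit are those above it at both baselines and again on extension treatment, about 1-5 of 180 at 450 msec.

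Mean, SD, correlation and absence of a drug effect are all assumptions.

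**What to change.** In SAP 17.3, beside the existing new-onset rows, add the number and percentage of subjects with any post-OL-baseline QTcF or QTcB above 450, 480 and 500 msec regardless of baseline, including unscheduled visits as the current rows do. In SAP 3.7, add one bullet stating that the new-onset definition is an addition to the protocol's count. No extra row is needed for rises of at least 30 msec.

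The cost is three table rows for each QT correction and one bullet, with no new data. The one drawback is that a figure that may be slightly less favourable will stand next to the current one.
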